13.5 Notification of AEs of Special Interest (AESIs)

Not applicable.

13.6 AEs that do not require reporting

AEs or SAEs that are expected and do not require reporting for this trial are taken from the SmPC. However, AEs and SAEs that are defined as DLT events (Table 1) will be reported.

Similarly, considering that all eligible patients are critically ill and at increased risk of experiencing multiple AEs, the below list defines possibly and definitely expected AEs or SAEs related to organ failure and critical illness which are exempt from regulatory reporting.^{11 43}

AEs or SAEs not requiring reporting in this trial:

Prolonged bleeding time, fishy taste, headaches, circulatory effects (e.g. hypo/hypertension), rash, abdominal pain, nausea, vomiting, rise in body temperature or fever, shivering, chills, tiredness, transient increase in liver function tests, metabolic overload symptoms (hepatomegaly with or without icterus, change in reduction in bleeding time, coagulation time, prothrombin time, splenomegaly, headache, stomach pains, fatigue, hyperglycemia), dyspnoea, chest pain, hypoxaemia, rapid pulse, rapid respiratory rate, dizziness, syncope, altered mental status, seizure, confusion, anxiety, generalised weakness, anorexia back pain, constipation, pneumonia, skin infection, cancer, electrocardiography abnormalities (atrial arrhythmias, right bundle branch block, and ST and T wave changes), elevated troponin level, elevated BNP or NT ProBNP level, high white cell count, pulmonary infiltrate, pleural effusion, cardiomegaly, shock, worsening organ failure, or sepsis.

13.7 Notification and reporting of Serious Adverse Events (SAEs) and Suspected Unexpected Serious Adverse Reactions (SUSARs)

All SAEs, apart from those listed in 13.6 and SUSARs will be recorded in the participants' notes, the eCRF, the sponsor SAE form and reported to the sponsor (administered by the Joint

Research Management Office (JRMO) or agreed representative) and the IMP provider (as per contract with the funder/manufacturer) within 24 hours of the site becoming aware of the event.

Nominated co-investigators (as listed) will be authorised to sign the SAE forms in the absence of the PI at the participating site.

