13.2 Site investigator assessment

The PI, who is also the CI for this trial, is responsible for the care of the participant, or in their absence an authorised medic within the research team is responsible for assessment of any event for:

Seriousness

Assessing whether the event is serious according to the definitions given in section 13.1.

Causality

Assessing the causality of all SAEs and SARs in relation to the study treatment according to the definition given. If the SAE is assessed as having a reasonable causal relationship, then it is defined as a SAR.

Expectedness

Assessing the expectedness of all SARs according to the definition given. If the SAR is unexpected (as per the reference safety information), then it is a SUSAR.

Severity

Assessing the severity of the event according to the following terms and assessments. The intensity of an event should not be confused with the term "serious" which is a regulatory definition based on participant/event endpoint criteria.

Mild: Some discomfort noted but without disruption of daily life

Moderate: Discomfort enough to affect/reduce normal activity

Severe: Complete inability to perform daily activities and lead a normal life

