13.3 Reference Safety Information

Reference safety information can be found in the SmPC under section 4.8.

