13.8 Sponsor medical assessment

Sponsor has delegated the responsibility for oversight of IMP safety profile and medical assessment of AEs, ARs, SAEs and SUSARs to the CI as medical assessor. The CI must review all SAEs within 72 hours of receipt. This review should encompass seriousness, relatedness, and expectedness. Day 0 for all SUSARs is when the SAE / SUSAR is received by the CI and / or coordinating team and / or Sponsor (whichever is first).

It is noted that the CI cannot downgrade the PI assessment of an event's causality. If there is disagreement between CI and PI assessment, no pressure should be placed on the PI to alter their assessment, but the CI can liaise with the site PI before the CI's final decision. The CI and PI assessment can differ.

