14.0 Annual reporting

14.1 Development Safety Update Report (DSUR)

The DSUR will be written by the CI (following Sponsor procedures) and submitted to the sponsor for review prior to submission to the MHRA. The DSUR is due for submission within 60 days of the end of the reporting period. The reporting period is annually from the date on the "Notice of acceptance letter" from the MHRA. The sponsor's delegated Medical Assessor, usually the CI, will carry out a risk benefit analysis of the IMPs encompassing all events having arisen on the study. REC will be sent a copy of the DSUR.

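### Section 13.6 exempts listed serious events by term, with no causality condition, so a possibly Omegaven-related listed event can be a SUSAR under 13.1–13.3 and exempt under 13.6

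*Protocol*

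**What the plan says.** Section 13.6 builds its exemption from two sources. The first is the product information: "AEs or SAEs that are expected and do not require reporting for this trial are taken from the SmPC". The second is the patients' condition: "the below list defines possibly and definitely expected AEs or SAEs related to organ failure and critical illness which are exempt from regulatory reporting". Both feed one continuous list, introduced as "AEs or SAEs not requiring reporting in this trial". It runs from fishy taste and metabolic overload symptoms to seizure, pneumonia, shock, worsening organ failure and sepsis. The one stated exception is that DLT events in Table 1 are reported.

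Section 13.4 requires AEs and adverse reactions (ARs) to be documented in the notes and the eCRF unless they are on the 13.6 list. Section 13.7 sets the 24-hour report to the sponsor and the IMP provider, and begins: "All SAEs, apart from those listed in 13.6 and SUSARs will be recorded".

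Expectedness is defined separately. Section 13.2 says: "If the SAR is unexpected (as per the reference safety information), then it is a SUSAR". Section 13.3 says: "Reference safety information can be found in the SmPC under section 4.8". The SUSAR definition in 13.1 uses the same standard, covering both nature and severity.

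**The concern.** The protocol uses the word expected in two senses. In 13.1–13.3 it means consistent with SmPC 4.8. In 13.6 it also means foreseeable in a critically ill patient. The second sense suits background events in intensive care, but only while they are judged unrelated to the drug. Once an investigator thinks that Omegaven may have contributed, the event is a reaction and SmPC 4.8 should decide whether it is expected. Section 13.6 does not say that such an event leaves the exemption.

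This matters because the trial is a safety study. Sections 1.3 and 6.2 deliberately admit patients with conditions that the SmPC lists as contraindications, and 6.2 calls existing safety data scarce. The top dose of 0.6 g/kg/d is three times the upper end of the 0.1–0.2 g/kg/d guideline range cited in 1.1 (0.6 / 0.2 = 3). A new serious reaction in these patients could well present under terms on the list. Later reviews depend on what is sent or recorded. Section 13.8 says "The CI must review all SAEs within 72 hours of receipt", and the DSUR risk-benefit analysis in 14.1 is described as "encompassing all events having arisen on the study".

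**Working it through.** The plan gives no figure for this point. The check sets the rules side by side, with one count and one piece of arithmetic on the DLT window.

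1. **Size of the list.** Splitting 13.6 at commas, with each bracketed group kept as one item, gives 41 terms or term groups. It is 42 if the run-together anorexia and back pain are separated, and 54 if bracketed sub-items count separately.

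2. **Is the exemption limited by cause?** The lead-in describes the events as related to organ failure and critical illness. That limit is not carried forward:
   - The list heading has no condition.
   - The list also contains drug effects, so the lead-in cannot describe every item.
   - Section 13.4 applies the exemption to ARs. Section 13.1 defines an AR as related to the IMP, with causality at least a reasonable possibility. So 13.4 expressly exempts some related events from recording.
   - Section 13.7 refers back to 13.6 without adding a condition.

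3. **The same event under both rules.** Take a serious seizure that Omegaven may reasonably have caused, and assume that it is not consistent with SmPC 4.8.

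| Rule | Result |
|---|---|
| 13.1–13.3 | Related and serious, so a SAR; unexpected against SmPC 4.8, so a SUSAR |
| 13.4 | Listed, so recording is not required |
| 13.6 | Listed, so reporting is not required unless it is a Table 1 DLT |
| 13.7 | Depends on how the sentence is read |

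4. **The 13.7 sentence.** Reading A: all SAEs except the 13.6 ones are reported, and SUSARs are reported. Reading B: the 13.6 SAEs and SUSARs are both excepted. The section heading names SAEs and SUSARs as the two reportable classes, and 13.8 sets a Day 0 for every SUSAR. Both favour A. Under A the event is reportable under 13.7 and exempt under 13.6, which is a contradiction.

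5. **The DLT exception.** None of the named rows of Table 1 (haemolysis, hypertriglyceridaemia, reticulocytosis, thrombocytopenia, thrombophlebitis, urticaria) covers seizure, shock, sepsis or worsening organ failure. These can enter only as Other, which has these limits:
   - Severity: CTCAE grade 3 or higher.
   - Relatedness: Section 2.6 counts only definite or probable/likely. Possible is not enough, although a reasonable possibility suffices for an AR.
   - Timing of the decision: the panel meets after each dosing phase, not within 24 hours.
   - Onset: during the infusion or within 5 hours of its end.

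   The onset window follows from the 10 g/100 ml product (Section 11.1) and the initial rate of 0.5 ml/kg/h (Section 7.0). Hours of infusion = dose in g/kg ÷ 0.1 g/ml ÷ 0.5 ml/kg/h. At 0.6 g/kg this gives 12 hours, which matches the example in Section 7.0.

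| Dose (g/kg/d) | Infusion (h) | Window, infusion + 5 h | Outside the window, of 24 h |
|---|---|---|---|
| 0.2 | 4 | 9 | 15 |
| 0.4 | 8 | 13 | 11 |
| 0.6 | 12 | 17 | 7 |

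   A slower rate would lengthen the window.

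**The case against.** The strongest reply is that classification comes first. Section 13.2 requires causality to be assessed for every SAE and SAR, and expectedness for every SAR against the SmPC. Nothing in 13.6 says that it replaces that standard. A related, unexpected listed event becomes a SUSAR and, on the natural reading of 13.7, is reported within 24 hours. The missing comma in 13.7 is then a copy-edit. This stands in large part. A reader might infer that the protocol exempts SUSARs outright, but the 13.7 heading and the Day 0 rule in 13.8 do not support that.

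A reader might also infer that listed events are exempt whatever their cause. The lead-in to 13.6 points the other way for the critical-illness terms, and the mention of the SmPC explains why drug effects share the list. What remains is that no operative rule states this limit, and 13.4 runs against it by exempting listed ARs.

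The DLT route is not trivial either. At the top dose it spans 17 of 24 hours (71%), and Table 1 has staff contact the Chief Investigator, who is also the sponsor's delegated medical assessor. One could read 13.6 as triggered when Table 1 criteria are met, before adjudication. Even so, the grade threshold and the onset window still leave events out.

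Finally, Section 8.2 collects infections, SOFA score and mortality from all participants, so some listed conditions will appear in the data. They would not appear there as causality-assessed safety reports.

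**Conclusion.** The point holds as a conflict between rules. Sections 13.4 and 13.6 exempt by term. Sections 13.1–13.3 classify by relatedness and SmPC 4.8. Section 13.7 does not clearly say which prevails. The events at issue are serious listed events with a reasonable possibility of being caused by Omegaven that are not consistent with SmPC 4.8. Within that group, the DLT exception does not reach events judged only possibly related, those below grade 3, or those with onset outside the Other window.

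Two limits apply. The SmPC is not at hand, so whether seizure, shock or sepsis is absent from section 4.8 cannot be checked; the worked example is conditional on that. The documents give no rate of Omegaven-caused listed events, so the number affected cannot be estimated. The count of 41 describes the breadth of the exemption, not the expected loss, and many of its terms are rarely serious. The protocol should be corrected because this is a safety trial and the correction is cheap.

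**What to change.** Change the wording in three sections:

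- **13.6:** limit the critical-illness exemption to listed events judged to have no reasonable possibility of being caused by Omegaven. State that the list does not replace SmPC 4.8 for judging expectedness. Marking which terms come from the SmPC and which from critical illness would make the limit workable.
- **13.4:** require listed events judged related (ARs) to be recorded.
- **13.7:** reword to: *All SAEs (except those exempt under 13.6) and all SUSARs, including any whose term is listed in 13.6, will be recorded and reported.*

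Serious reactions that are expected under SmPC 4.8 can stay exempt, as the protocol intends; 24-hour reporting of every SAR is not needed to resolve the conflict. Unrelated background events of critical illness also stay exempt. The cost is a protocol amendment to the text, some additional recording of listed reactions, and a few more 24-hour reports.

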13.8 Sponsor medical assessment

Sponsor has delegated the responsibility for oversight of IMP safety profile and medical assessment of AEs, ARs, SAEs and SUSARs to the CI as medical assessor. The CI must review all SAEs within 72 hours of receipt. This review should encompass seriousness, relatedness, and expectedness. Day 0 for all SUSARs is when the SAE / SUSAR is received by the CI and / or coordinating team and / or Sponsor (whichever is first).

It is noted that the CI cannot downgrade the PI assessment of an event's causality. If there is disagreement between CI and PI assessment, no pressure should be placed on the PI to alter their assessment, but the CI can liaise with the site PI before the CI's final decision. The CI and PI assessment can differ.

13.9 Procedures for reporting blinded SUSARs

Not applicable as there will be no blinding.

13.10 Urgent safety measures

The CI may take urgent safety measures to ensure the safety and protection of the clinical study participants from any immediate hazard to their health and safety, in accordance with Regulation 30 of the Medicines for Human Use (Clinical Trials) regulations. The measures should be taken immediately. In this instance, the approval of the Competent Authority prior to implementing these safety measures is not required.

The CI has an obligation to inform both the MHRA and Research Ethics Committee (REC) in writing within 3 days of implementing the Urgent Safety Measure. They must also submit a substantial amendment documenting the changes with 14 days of implementing the urgent safety measure. The JRMO must be sent a copy of the correspondence with regards to this matter as soon as it is sent.

13.11 Pregnancy

There is no evidence on the safety of this medicine during pregnancy or breastfeeding. Therefore, pregnant patients will be excluded from the trial. As per hospital policy, female patients of childbearing potential (16-55) will receive a routine pregnancy test at critical care admission. These results will be considered when screening patients for eligibility to be included in the trial and pregnant patients will be excluded from participation. Any unexpected pregnancies occurring during the administration of the IMP is not considered to be an SAE or an AE and will be reported per Sponsor SOP and followed up to term. The Sponsor should be notified immediately (within 24 hours of site becoming aware of the pregnancy), using the Sponsor pregnancy form. Follow-up information should be submitted as and when it becomes available up to the birth of the infant. Any events to the mother or child that occur during the pregnancy until birth that could be considered to be a SAE must be reported to the Sponsor in line with section 13.7 using the Sponsor SAE reporting from. The Sponsor will arrange for a review of the pregnancy report by an appropriate expert medic (usually a consultant obstetrician). The study team must follow all instructions provided by the Sponsor's expert. The pregnancy reporting procedure will be the same as the SAE reporting route. If a pregnancy is confirmed during the trial IMP administration phase, the IMP will be stopped, if ongoing, as soon as the study team becomes aware of the pregnancy and the participant will be withdrawn from the trial. In this case the participant will be replaced. Pregnancies conceived after the 11 days of IMP administration will not be followed up due to the short half-life of the IMP (54 minutes).

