5.0 Participant allocation

Since the trial involves an IMP that is unlicensed in UK, the PI or delegated doctors will be required to confirm eligibility of patients identified by the research team in the medical notes prior to approach. Following written informed consent, the patient will be randomised to either the standard care or Omegaven arm in blocks of 12 patients per dose-escalation phase. All randomised patients will be recorded on the study enrolment log with their trial ID.

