6.2 Exclusion criteria

We are specifically not excluding patients with acute life-threatening conditions such as collapse or shock, recent cardiac infarction, stroke, embolism, undefined coma status, severe haemorrhagic disorders or severe liver or renal insufficiency as indicated in the SmPC. We seek to test the safety of Omegaven in critically ill patients (who suffer from these conditions) as part of a new set of indications. The SmPC notes that some of these are considered contraindications as a result of lack of experience, which we seek in this safety trial to inform. In previous studies, Omegaven has been given therapeutically to critically ill patients before, in the UK ^{19 20}, and in- and outside the EU^{17 18 22 23}, but safety data are scarce. A safety trial such as the one we are proposing is necessary prior to a larger efficacy trial.

Exclusion criteria (as defined in the patient's medical notes):

- Patients requiring total parenteral nutrition at time of enrolment or during the first 10 days.
- Palliative care admission for end-of-life care or withdrawal of active therapy as determined by the Intensive Care Consultant with clinical responsibility for patient care.
- Neutropaenia (<1x10⁹/l) on admission to the Adult Critical Care Unit
- Lymphopenia (<0.25x10⁹/l) on admission to Adult Critical Care Unit
- Primary immune deficiency
- Bone marrow transplant recipient
- All immunosuppressive drug therapy (with the exception of corticosteroid use for acute illnesses in the preceding five days)
- Recorded or reported allergy to fish, or egg protein or to any of the active ingredients or excipients
- Known inborn errors of lipid metabolism

- Recorded or reported severe hyperlipidaemia or severe disorders of lipid metabolism
- Electronic health record documentation ± clinical concern and if available: serum triglycerides >400 mg/dl on admission to the Adult Critical Care Unit
- Enrolment in any other study with an IMP or a study that may have similar primary outcome
- Therapeutic anti-coagulation therapy
- Pregnancy

The absence of the above criteria in the medical notes will be considered to indicate no concern.

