To verify fish or egg allergies, the electronic patient record will be checked when confirming eligibility. Clinical decision making will also be utilised. If patients are receiving standard enteral feed (Fresubin Original), containing fish oil they are deemed not to have a fish allergy. We will also talk to the clinician with clinical responsibility for patient care asking if there is any concern of an egg or other allergy from any communications from relatives or friends.

Patients in ICU are continuously monitored by the bedside nurse, who will pick up and react to possible signs of allergic reactions. Additionally, the research nurses administering Omegaven will stay at the patient's bedside and monitor the patient every 5 minutes for the first half an hour after the first administration of Omegaven, to make sure administration is of no concern.

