8.2 Trial and follow-up assessments

The following assessments will be done in all participants:

Eligibility

- Screening for inclusion and exclusion criteria
- Medical history
- Informed consent

Randomisation (within 48 hours of admission to critical care)

- Participant Initials
- Trial ID (generated automatically at the point of randomisation)

Baseline data

- Age
- Sex at birth
- Medical history

Day 1-Day 10 or hospital discharge

- IMP administration and details (intervention arm only)
- Safety review

DLT assessment

Day one continuing daily until day 11

Blood samples

- Before start of intervention (within 48 hours of admission to critical care)
- Day five from start of intervention
- Day 10 from start of intervention
- Day 20 from start of intervention; censured at hospital discharge

Routinely collected data

- Medical note review for
 - Infections
 - o Clinical Pulmonary Infection Score
 - o Antibiotic free days
 - Ventilator free days

- Mortality
- Length of critical care stay
- Length of hospital stay
- o Length of hospital stay before Adult Critical Care Unit admission
- Critical care level received
- Steroid free days
- Renal replacement therapy free days
- Enteral feed intake
- Bristol Stool Score
- SOFA score
- Laboratory values
- Blood transfusions
- Hospital admission

Follow-up phone call at 30 days

- o Antibiotic prescriptions after hospital discharge
- o Use of omega-3/nutritional supplements in the 3 months prior to hospitalisation
- Ethnicity

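### Section 6.2's rule that an exclusion not found in the notes is no concern also covers pregnancy, so a missed, pending or unrecorded test counts as the exclusion not being met

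*Protocol*

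**What the plan says.** Section 13.11 gives the reason for the exclusion, "There is no evidence on the safety of this medicine during pregnancy or breastfeeding", and the means of detection: under hospital policy, "female patients of childbearing potential (16-55) will receive a routine pregnancy test at critical care admission". On how the result is used, it says "These results will be considered when screening patients for eligibility to be included in the trial" and that pregnant patients will be excluded.

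Section 6.2 introduces its list with "Exclusion criteria (as defined in the patient's medical notes". Pregnancy is the last item. The list closes with "The absence of the above criteria in the medical notes will be considered to indicate no concern". The synopsis has the same list and the same closing rule.

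Section 5.0 adds a sign-off: "the PI or delegated doctors will be required to confirm eligibility of patients identified by the research team in the medical notes prior to approach". Section 8.1 has one row for eligibility review, and section 8.2 has one general item, "Screening for inclusion and exclusion criteria". Neither these sections nor section 5.0 says what follows when a pregnancy result is not there.

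**The concern.** The two sections treat silence in the notes differently. Section 13.11 presumes that a result exists and is looked at. Section 6.2 supplies an answer when nothing is recorded, and the answer is that there is no concern. For a diagnosis such as primary immune deficiency, a clean record is some evidence that the condition is absent. For pregnancy, an empty record may mean only that the test was not done, has not been reported or was not entered.

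What is at stake is participant safety. The protocol itself says there is no safety evidence in pregnancy. Section 4.0 says that critical care patients are frequently unable to consent for themselves, and in those cases a professional legal representative consents first and a relative or friend is approached later. Section 7.0 starts the intervention within 48 hours of critical care admission. For such patients, a recorded test is the most dependable safeguard that the plan describes before the first dose.

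**Working it through.** No arithmetic applies; the check is to read the provisions together.

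1. *Which criteria does the default cover?* The closing sentence of 6.2 refers to the criteria above it. Pregnancy is one of them, and neither 6.2 nor the synopsis carves it out.

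2. *What does 13.11 require?* It expects a test for women aged 16 to 55, which in this trial means 18 to 55 because section 6.1 sets a minimum age of 18. It requires the results to be considered. It does not say that a result must be on file, and it has no rule for a missing one.

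3. *Does another section close the gap?* Section 5.0 requires a doctor to confirm eligibility from the notes but does not name a pregnancy result as a condition. Sections 8.1 and 8.2 list eligibility screening in general terms. Section 13.11 provides for a pregnancy confirmed during dosing, but that is after exposure.

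4. *Apply the text to each case.*
   - Positive result recorded: the exclusion is met under both sections.
   - Negative result recorded: the exclusion is not met under either section.
   - No result recorded: 13.11 has nothing to consider; 6.2 says no concern; the exclusion is not met. If the other criteria are satisfied, the woman can be randomised, and she is dosed if allocated to Omegaven.

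   Only the third case is a problem, and there the only rule that gives an answer is the default in 6.2.

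5. *Does the protocol handle missing routine data elsewhere?* It does. Section 2.6 says that laboratory measures for dose-limiting toxicity will be mandated by the research team when routine care has not provided them. The triglyceride criterion in 6.2 is worded to apply only if a value is available. For allergy, 6.2 adds a further step, "To verify fish or egg allergies, the electronic patient record will be checked when confirming eligibility", together with a conversation with the responsible clinician. Missing routine data were thus foreseen in several places, but no rule was written for a missing pregnancy result.

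**The case against.** The strongest reply is that the sections work together. Section 13.11 is the specific provision: the whole at-risk group is tested, the result is considered and pregnant patients are excluded. The sentence in 6.2 is a general default, suited to history-type criteria that may never have been written down. A sensible screener would look for the result, and the confirming doctor is a second check. The gap then needs a failure of hospital policy or of recording, and two people who miss it.

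Much of this stands. The gap is narrow, and good practice would often close it. But the protocol does not say that 13.11 overrides 6.2, and enrolling a woman without a result would comply with 6.2 as written. An explicit default that gives the wrong answer for a missing test is more than an omitted detail.

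A reader might infer four stronger things that the documents do not support:

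- *That pregnancy has no verification step, unlike allergy.* Section 13.11 is one, and an objective test is arguably firmer than the allergy check. What is missing is a rule for an absent result.
- *That each missed pregnancy costs its dose cohort a patient.* Section 13.11 says the participant will be replaced, and no effect on the toxicity rate or the selected dose has been shown.
- *That 6.2 and 13.11 conflict on breastfeeding.* Section 13.11 mentions the lack of evidence for both states but draws an exclusion only for pregnancy, and 6.2 agrees with that.
- *That the lack of a separate pregnancy row in 8.1 or 8.2 is itself an error.* The neutrophil, lymphocyte and triglyceride exclusions have no eligibility row of their own either.

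**Conclusion.** The concern holds in a limited form. As written, 6.2 and the synopsis class a missed, pending or unrecorded pregnancy test as the exclusion not being met, and no section makes a result a condition of randomisation. This should be corrected because the possible harm is serious and the correction is small.

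The size cannot be estimated. The documents do not give the share of participants who will be women in the tested age range, the rate of missing results at screening or the prevalence of pregnancy in this population. A count built on assumed values would measure untested women and not exposed pregnancies, and only the 27 of 36 participants planned for Omegaven would be dosed. The conclusion rests on a literal reading of 6.2 and on the possibility that a routine test is sometimes not on record when eligibility is confirmed. It does not rest on any claim about how often that happens.

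**What to change.** Reconcile 6.2 and the synopsis with 13.11. Take pregnancy out of the absence-means-no-concern default for the women whom 13.11 says are tested, and cross-refer to 13.11, so that the eligibility confirmation in 5.0 rests on the recorded result of the routine test and not on the lack of an entry.

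The cost is about one sentence in 6.2 and the same sentence in the synopsis. No new procedure is needed, because 13.11 already describes the test as routine. The downside is that randomisation may occasionally have to wait for a result within the 48-hour window.
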